11.0 Provisions to Monitor the Data to Ensure the Safety of Subjects

A DSMB will ensure the safety of participants and the validity and integrity of data collected. The overall framework involves review of the enrollment/retention and safety and adverse event data by the DSMB during the proposed research.

DSMB composition: The DSMB will be composed of three professionals with expertise related to the proposed area of study who are not involved with the study design or experiments. Specifically, the DSMB will include: (1) a board-certified stroke neurologist who also is a researcher and is experienced in care of chronic stroke survivors and their recovery; (2) a registered and licensed occupational therapist who also is a researcher; and (3) a biostatistician with expertise in design and analysis of clinical trials. This multidisciplinary group has experience with management and monitoring of clinical intervention trials involving individuals following stroke, and brings substantial expertise adequate to serve as the DSMB.

DSMB responsibilities: The responsibilities of the DSMB are as follows.

- Prior to any enrollment, the DSMB will review the study design, protocol, informed consent documents, amendments, recruitment/enrollment plan, statistical analysis plan, and data and safety monitoring plan, and document the agreement or recommendation.
- Once the enrollment begins, the DSMB will convene every 6 months to review the progress of the trial.
- The DSMB will review the enrollment/retention data including new enrollments, progression of the enrollees' participation in the study, any discontinuation of participation in the study with or without adverse events, and the current enrollment status compared to the project time line.
- The DSMB will review data quality and quality control data.
- The DSMB will review safety and adverse event data. The DSMB will review the aggregated summary data as well as the individual participants' data (de-identified). The DSMB will discuss participant risk vs. benefit and other factors that may potentially affect study outcomes. The DSMB will make recommendations for appropriate action to maintain a reasonable safety profile for the study.
- The DSMB will ensure that all serious adverse events have been followed to resolution, and that the appropriate agencies (including the IRB and/or federal funding agency) have been informed.
- The DSMB will advise the IRB and the study investigators as to whether the protocol should continue as scheduled or undergo any modification due to findings from the monitoring process. The DSMB may recommend stopping the study early if the study has unanticipated safety concerns that warrant stopping.
- The DSMB will review study performance as well as make recommendations and assist in resolution of problems reported by the PI.
- The DSMB will ensure the confidentiality of the study data and the results of monitoring.
- The DSMB will document their reviews in writing and provide a report to the IRB to summarize oversight activities, recommendations and any concerns regarding participant safety. The report will include participant characteristics (including distributions across race and sex), retention and disposition of study participants, quality assurance issues and reports of adverse events, significant/unexpected adverse events and serious adverse events.
- The DSMB will review final analysis results upon completion of the data collection.

Reporting of safety data: All serious adverse events will be reported to the IRB as they occur. All enrollment/retention data and safety and adverse event data will be reported to the DSMB during the review. The DSMB will review the data and submit a report to the IRB. Summative safety data will be reported to ClinicalTrials.gov and in publications. As such, we will register this study in ClinicalTrials.gov as soon as the study commences and report results including all adverse events as soon as the study is completed following the guidelines. To protect participants' confidentiality, personally identifiable information will not be used for reporting. Only de-identified or aggregated data will be used for reporting.

12.0 Withdrawal of Subjects

Subjects who do not show up on scheduled visits or do not complete the intervention in 10 weeks may be withdrawn by the investigator. Subjects who are or become medically unstable may be withdrawn by the investigator. For those who withdraw from the research, their data collected up to that point may be used by the investigator.

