9.0 Study Design / Methods

Study design: The study design is a double-blinded randomized controlled study. Participants will undergo standardized hand task practice therapy (3 sessions/week for 6 weeks) with the watch worn on the paretic wrist. Participants will be randomized into two groups: The device will deliver vibration for the treatment group and no vibration for the control group during therapy. Half the participants will be in the treatment group, and half in the control group. Double blinding is possible since treatment vibration is imperceptible (i.e., subthreshold). Evaluation will be performed at baseline, after 2, 4, and 6 weeks of continuous task practices and at 1-month follow-up.

Schedule: Participation will last 2.5 months. Participants' involvement entails 18 visits for therapy (each lasting 1-2.5 hours, 3 sessions/week for 6 weeks) and 2 evaluation visits (evaluations at each time point divided into 2 visits to minimize fatigue) for each of the 3 time points (baseline, after therapy, and follow-up), along with one time only, 30-min MRI assessment, resulting in a total of 25 visits over 2.5 months. Each activity is described below.

Therapy: Participants will undergo a standardized hand task-practice therapy program. Upper limb tasks for activities of daily living that are of the participants' interests and are related to participants' goals will be chosen and practiced with repetitions, in the laboratory. The difficulty level of the tasks will be modified per participants' progress. To translate improved motor capacity to independence at home, the paretic hand use in daily tasks at home will be tracked and encouraged.

Evaluation: Each of the two evaluation visits will last approximately 2-5 hours. The following assessments will be performed across the two evaluation visits.

Upper limb function assessment: Clinical upper extremity function scores will be assessed using conventional clinical assessments used in occupational/physical therapy in which participants will be asked to move the affected hand and arm, grasp objects and perform prescribed tasks (e.g., lifting an object off the table, releasing the object into a bin) as quickly as possible or at a comfortable speed, upon cues. These tests

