10.0 Data Management

Recruitment: Recruitment projects are housed in REDCap. Only study personnel will have access to the REDCap database while actively enrolling for the study.

Analysis: The primary analysis will be a repeated measures ANOVA for each outcome. The dependent variables will be the change from baseline at the evaluation times. The primary independent variables are group, evaluation time, and their interaction. We will also include sex as a biological independent variable along with its interactions. If the group by time interaction is significant, we will examine if there is a group difference at 10 weeks using post-hoc tests.

Sample size justification: The clinically meaningful difference in time needed to complete a functional upper limb task is deemed to be 4 to 7 s. This study will be powered to detect difference at follow-up of at least 4s in movement time between the treatment and control groups. For the repeated measures design with a significance level of 0.017 (adjusted for multiple comparison), at least 80% power, and 4 time points, for a standard deviation (SD) of 5.1s and compound symmetry correlation of 0.92 (both based on our pilot study²⁹), sample size of 32/group will be adequate. Adjusting for 15% attrition, 38/group is planned (total n=76).

Confidentiality: All data except for the consent forms and HIPPA forms will be coded at the time of data recording. All electronic data will be stored in a password-protected research server that is accessible to study personnel only. Videos of the upper limb movement will be recorded such that we will avoid capturing the participant's face, while capturing the hand, arm, and object being gripped. All paper data with personally identifiable information including the consent forms and HIPPA forms will be stored in a key-locked cabinet in a key-locked room that is accessible to study personnel only. Other paper data without personally identifiable information including testing sheets documenting testing sequences and notes will also be stored in a cabinet in a key-locked room that is accessible to study personnel only.

Data sharing: Only de-identified coded data will be reported and/or shared with the public and other investigators

in publications, in ClinicalTrials.gov, or via data depository.

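### Randomised participants can be withdrawn for missed visits or slow therapy, with no later assessment planned and no analysis set or missing-data method stated

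*Combined protocol and SAP*

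**What the plan says.** Section 12.0 (Withdrawal of Subjects) states: "Subjects who do not show up on scheduled visits or do not complete the intervention in 10 weeks may be withdrawn by the investigator". It also allows withdrawal of medically unstable participants. For anyone who withdraws, it says that "their data collected up to that point may be used by the investigator". Failing to finish the intervention can only happen once therapy is under way, so the rule reaches randomised participants.

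Section 10.0 (Analysis) states: "The primary analysis will be a repeated measures ANOVA for each outcome". It continues: "The dependent variables will be the change from baseline at the evaluation times". If the group-by-time interaction is significant, "we will examine if there is a group difference at 10 weeks using post-hoc tests". Loss of participants appears only in the sample size paragraph: "Adjusting for 15% attrition, 38/group is planned (total n=76").

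Section 9.0 gives the evaluation times twice. Under study design: "Evaluation will be performed at baseline, after 2, 4, and 6 weeks of continuous task practices and at 1-month follow-up". Under schedule, two evaluation visits are planned "for each of the 3 time points (baseline, after therapy, and follow-up"), giving 25 visits over 2.5 months.

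Section 11.0 has the DSMB review retention and discontinuations, and lists a statistical analysis plan among the documents it sees before enrolment. The only analysis text in the document under review is the paragraph in section 10.0.

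**The concern.** The grounds for withdrawal concern adherence, and adherence may be related to recovery. The comparison of interest is at the 1-month follow-up, which is the evaluation a withdrawn person would miss. The wording on earlier data permits its use without committing to it. The term repeated measures ANOVA does not show whether people with some missing evaluations are kept or dropped. Who enters the 10-week comparison is therefore not fixed in advance, and it could be a more adherent subset of those randomised. Enrolling more people does not turn that subset back into a randomised comparison.

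Movement time is better when shorter. Losing poorer responders from the vibration arm would flatter vibration; losing them from the control arm would hide a benefit.

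**Working it through.** **1. The plan's own sample size.** Inputs from section 10.0: difference 4 s, SD 5.1 s, correlation 0.92, 4 time points, significance level 0.017 (two-sided assumed), power 80%. Comparing the arms on the mean of 4 time points under compound symmetry:

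- SD of the mean = 5.1 × √((1 + 3 × 0.92)/4) = 4.945 s
- n per group = 2 × (4.945 × (2.387 + 0.842)/4)² = 31.85, rounded up to 32 (power 80.2% at 32)
- 32/0.85 = 37.6, rounded up to 38 per group, 76 in total

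The stated figures reproduce. Attrition is covered for power only.

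**2. Bias if lost participants are left out.** The documents give neither a loss pattern nor an outcome gap, so both are assumed here. In each arm, the mean of those kept differs from the mean of all randomised by −(share lost × gap between lost and kept). The bias is the difference of that product between arms.

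The SD of change depends on what 5.1 s refers to:

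- If it is the SD of change: 5.1 s.
- If it is the SD of raw scores: 5.1 × √(2 × (1 − 0.92)) = 2.04 s.

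The standard error at 32 per group, single time point, is 5.1 × √(2/32) = 1.275 s or 2.04 × √(2/32) = 0.51 s.

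| Assumed loss, 1 SD gap | Bias (SD 2.04 to 5.1 s) | Share of 4 s | Shift in standard errors | Two-sided type I error |
|---|---|---|---|---|
| Equal informative loss in both arms | 0 | 0 | 0 | 0.017 |
| 5-point imbalance | 0.05 × SD = 0.10 to 0.26 s | 2.6% to 6.4% | 0.2 | 0.019 |
| Extreme: all 15% of one arm lost informatively, random loss in the other | 0.15 × SD = 0.31 to 0.77 s | 8% to 19% | 0.6 | 0.038 |

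**3. What a mixed model can recover.** If loss depends on the unobserved 10-week value itself, conditioning on one earlier evaluation leaves about 1 − r² of the bias. On the raw-score reading, the correlation between two change scores is 0.08/0.16 = 0.5, so 1 − 0.25 = 75% remains. If 0.92 applies directly, 1 − 0.92² = 15% remains. The model helps, but it does not replace collecting the outcome.

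**4. Cost of following everyone.** At 15% attrition, 0.15 × 76 = 11.4 people. Each has up to 4 after-therapy and follow-up visits (2 visits at 2 time points), so 11.4 × 4 = 45.6 visits. If the 15% who stop gain nothing, the effect is 4 × 0.85 = 3.4 s. With all 38 per group followed, the standard error is 4.945 × √(2/38) = 1.134 s, and 3.4/1.134 − 2.387 = 0.61, which is 72.9% power.

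**5. The schedule.** 18 therapy visits + 2 × 3 evaluation visits + 1 MRI = 25. Two visits at each of the 5 listed time points would give 18 + 10 + 1 = 29. So the week-2 and week-4 evaluations have no separate visits in the count. Follow-up after six weeks of therapy falls at 6 + 4 = 10 weeks. Someone whose therapy takes 10 weeks would reach it at about 10 + 4 = 14 weeks, beyond the stated 2.5 months.

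**The case against.** The strongest reply is that the effect is small and conjectural. Withdrawal is discretionary, no section excludes non-completers from the analysis, and earlier data may be used. The trial is double-blind with imperceptible vibration, so withdrawal decisions are unlikely to depend on arm, and the DSMB sees discontinuations. Most of this stands, and it is why the bias is described as small. It does not supply a missing outcome or say how one is handled. DSMB review is oversight, not an analysis rule.

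A separate analysis plan may also exist, since section 11.0 mentions one. If it states an analysis set and a missing-data method, that part of the point falls; the withdrawal wording in section 12.0 would remain.

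Following everyone has a price in power and settles what is being estimated. That stands and is counted in the cost.

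A reader might infer from the 25-visit count that anyone withdrawn during therapy has only a baseline, so that no model of change could use them. The documents do not support this. Section 9.0 expressly lists evaluations after 2 and 4 weeks, and the sample size uses 4 time points. The count shows only that those evaluations have no visits of their own. Section 3.0 gives therapy sessions of 1-2 hours and section 9.0 gives therapy visits of up to 2.5 hours. That leaves room for testing within a visit, although the purpose of the extra time is not stated.

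**Conclusion.** The gap holds and is worth closing. Adherence-based withdrawal, no provision for later assessment, and an analysis with no stated population or missing-data method leave the 10-week comparison open to selective loss that the 15% inflation cannot repair.

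The expected size is modest: no bias under equal informative loss, 0.10 to 0.26 s for the assumed 5-point imbalance, and 0.31 to 0.77 s only in a deliberately extreme case. These figures rest on an assumed 1 SD gap and on either reading of the 5.1 s SD.

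It would go too far to say that the result will be a completers-only comparison or that it will be biased; the text leaves that possible but does not prescribe it. This is an inexpensive improvement, not a flaw that undermines the trial.

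**What to change.** 1. **Section 12.0.** State that participants who stop, miss or overrun therapy remain in the study and are invited to the remaining after-therapy and follow-up evaluations, unless they withdraw consent or the investigator judges assessment medically unsuitable. State that data already collected will be used where consent allows. For people who stop early, date these evaluations from the planned end of therapy (6 weeks after its start), and record actual dates. Who stops therapy is unchanged.
2. **Section 10.0.** Replace the repeated measures ANOVA with a likelihood-based mixed model of all randomised participants as allocated, using every available evaluation. Add one sensitivity analysis for loss that depends on unobserved outcomes.
3. **Reconcile.** Align the week-2 and week-4 evaluations in section 9.0 with its 3 evaluation time points and 25-visit count. Reconcile the 10-week therapy limit in section 12.0 with the 10-week comparison in section 10.0 and the 2.5-month participation in section 9.0.

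**Cost.** Wording in three sections, and at most about 46 recall visits, all already in the 25-visit schedule. The estimate will include people with incomplete therapy, and the plan should present this as a deliberate choice of what is estimated. In the worst case above, the effect falls to 3.4 s and power to about 73%, against 80.2% for a 4 s effect at 32 per group. Any benefit in those who stop would reduce that loss.

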13.0 Risks to Subjects

There is a slight risk for loss of confidentiality although researchers will take appropriate steps to protect any information collected about the participants.

There is a minor risk of physical and mental fatigue from engaging in the study activity. There is a minor risk of skin irritation from wearing the watch. There is a minor risk of discomfort in moving the arm/hand while wearing a watch on the wrist. There is a minor risk that subjects feel discomfort from wearing the accelerometer devices on their wrists for all day.

EEG: There is a minor risk of discomfort in wearing a head cap attached with a bundle of wires. Also, the gel used for the electrodes will get hair messy.

TMS: There is a serious risk that TMS could move iron-containing objects in or around the face or head, which in the process could possibly harm the person. There is a slight risk of a seizure with TMS; the incidence of seizures is very low and mostly associated with high frequency repetitive TMS (rTMS) which will not be used in this study. Instead we will use single-pulse TMS, which is much safer. There is a minor risk of scalp discomfort and headache. A TMS stimulus may feel like a slight tap to the skull. There may be discomfort from the muscle contraction that occurs in the hand muscle in response to the TMS. There is a very low risk of hearing loss due to the clicking sounds that the TMS machine makes. Safety of TMS in pregnancy is unknown. The use of tape or other adhesives to secure electrodes during testing may cause some mild skin irritation. Subjects with contraindications (e.g., epilepsy, metal in the head/neck, pregnancy) will not be tested for TMS. Subjects will be screened for safety before administering TMS (e.g., removal of all loose metal objects like earrings or nose rings).

MRI: There is a serious risk that MRI could move iron-containing objects in the MRI room, which could in the process possibly harm the person. The 3T MRI scanner is unsafe for pregnancy. There is discomfort by claustrophobia and by the loud banging noise. Temporary hearing loss has been reported from the loud noise from the MRI machine. The person may also feel uncomfortable as s/he will be asked not to swallow for a while. Subjects with contraindications (e.g., metal in the body such as a fragment in the eye, aneurysm clips, ear implants, spinal nerve stimulators, a pacemaker, or an implant electrical device, claustrophobia, pregnancy) will not be tested for MRI. Subjects will be screened for safety before entering the MRI room (e.g., removal of all loose metal objects like earrings or nose rings).

Potential risks that might be associated with use of wrist vibration include wrist skin irritation, increased upper limb pain, increased spasticity, weakness, and worsening of hand sensation or dexterity. These risks are expected to be rare because the intensity of vibration used is subliminal while we are exposed to higher-intensity, suprathreshold vibration daily (e.g. from a phone, car). Currently there is no vibration exposure guideline for this small level of vibration, as the U.S. Occupational Safety and Health Administration provides vibration exposure guidelines only for high-intensity vibration such as jackhammers and hand-held powered drills. Currently there are no known side effects using this small imperceptible level of vibration used in the proposed study. This vibration has been used for at least 8 hours daily for a month in chronic stroke survivors without safety concern in our pilot study. Nonetheless, safety will be systematically monitored at every visit.

14.0 Potential Benefits to Subjects or Others

There may be no benefit from participating in this study. The potential benefit is that the vibration the participant receives may help recover their hand function, although this cannot be guaranteed. Another potential benefit is that the hand therapy the participant receives may help recover their hand function,

although this cannot be guaranteed. The knowledge regarding the potential of using vibration as a therapy booster is important to improve hand function and activities of daily living for people who had a stroke and may benefit stroke survivors in general. The risks are deemed reasonable in relation to the potential gain of knowledge regarding this technology's efficacy in enhancing recovery of hand function after stroke and its associated neuroplasticity.

15.0 Sharing of Results with Subjects

If the subject agrees, the data collected and generated from this study will be shared to the Registry for Stroke Recovery (RESTORE-Pro#00037803) by the subject's registry ID. Sharing data from this study with the registry will allow for more targeted recruitment efforts in the future and allow researchers at MUSC to have a more complete registry with key stroke recovery elements including common data and physical function characteristics that are applicable to multiple studies. MUSC researchers and collaborating facilities will be able to query data sets to learn more about recovery of subjects after their stroke through institutionally managed secure servers that will assure HIPAA privacy and security compliance.

